## 7.2.2.2. Summaries of Laboratory Abnormalities

The following summaries (number and percentage of subjects) for treatment-emergent laboratory abnormalities will be provided by laboratory test and treatment group based on Safety Analysis Set for randomized phase analysis and All B/F/TAF Analysis Set for all B/F/TAF analysis, respectively; subjects will be categorized according to the most severe postbaseline abnormality grade for a given laboratory test:

- Treatment-emergent laboratory abnormalities
- Treatment-emergent Grade 3 and 4 laboratory abnormalities
- Treatment-emergent Grade 2, 3 and 4 laboratory abnormalities

For all summaries of laboratory abnormalities, the denominator is the number of subjects with any nonmissing postbaseline values up to 30 days after last dosing date.

A by-subject listing of all treatment-emergent laboratory abnormalities and treatment-emergent Grade 3 or 4 laboratory abnormalities will be provided by subject ID number and visit in chronological order.

## 7.2.3. Metabolic Laboratory Evaluations

For metabolic assessments, including fasting glucose and the lipid panel (ie, total cholesterol, triglycerides, LDL, HDL, total cholesterol to HDL ratio), only those measurements under fasting status will be summarized based on the Safety Analysis Set for randomized phase analysis and All B/F/TAF Analysis Set for all B/F/TAF analysis, respectively. P-values comparing the difference between the 2 treatment groups in baseline values and the change from baseline in metabolic assessment will be estimated from a 2-sided Wilcoxon rank sum test for randomized phase analysis. No formal statistical testing is planned for all B/F/TAF analysis.

For randomized phase analysis, the number and percentage of subjects who took lipid modifying medications at study entry and initiated the medications during the randomized phase of study will be provided by treatment group based on the Safety Analysis Set. Statistical comparisons of the subject incidence rates between the 2 treatment groups will be performed using Fisher's exact test. For all B/F/TAF analysis, the number and percentage of subjects who took lipid modifying medications at the First Dose of B/F/TAF and While Receiving B/F/TAF will be provided by treatment group based on the All B/F/TAF Analysis Set. No formal statistical testing is planned for all B/F/TAF analysis.

A lipid modifying medication is defined as a medication with drug class (based on the World Health Organization [WHO] Drug ATC2 term) = "LIPID MODIFYING AGENTS" and WHO Drug preferred drug name containing the wording of "STATIN".

For randomized phase analysis, a sensitivity analysis of fasting lipid tests will be performed by excluding subjects who took lipid modifying medications at study entry or initiated the medications during the study: baseline values, Week 48 values, and changes from baseline at Week 48 will be summarized by treatment group using descriptive statistics for randomized phase analysis. Baseline and change from baseline at Week 48 will be compared between the 2 treatment groups using a 2-sided Wilcoxon rank sum test for randomized phase analysis. Only subjects with both baseline and Week 48 postbaseline values will be included in the analysis.

Summary of baseline, postbaseline, and change from baseline in fasting metabolic laboratory tests will be repeated within each subgroup of baseline NRTI backbone (F/TAF vs. F/TDF) based on the Non-Study ARV Medication eCRF based on the Safety Analysis Set for randomized phase analysis. P-values comparing the difference between the 2 treatment groups in baseline values and the change from baseline in metabolic assessment will be generated from a 2-sided Wilcoxon rank sum test for randomized phase analysis.

Median (Q1, Q3) of change from baseline in fasting metabolic assessments over time will be plotted by treatment group based on the Safety Analysis Set for randomized phase analysis and All B/F/TAF Analysis Set for all B/F/TAF analysis, respectively.

## 7.2.4. Liver-Related Laboratory Evaluations

Liver-related abnormalities after initial study drug dosing will be examined and summarized using the number and percentage of subjects who were reported to have the following laboratory test values for postbaseline measurements based on the Safety Analysis Set for randomized phase analysis and All B/F/TAF Analysis Set for all B/F/TAF analysis, respectively:

- Aspartate aminotransferase (AST): (a) > 3 × Upper limit of normal (ULN), (b) > 5 × ULN,
   (c) > 10 × ULN, (d) > 20 × ULN
- Alanine aminotransferase (ALT): (a) > 3 × ULN, (b) > 5 × ULN, (c) > 10 × ULN,
   (d) > 20 × ULN
- AST or ALT: (a)  $> 3 \times ULN$ , (b)  $> 5 \times ULN$ , (c)  $> 10 \times ULN$ , (d)  $> 20 \times ULN$
- Total bilirubin: (a)  $> 1 \times ULN$ , (b)  $> 2 \times ULN$
- Alkaline phosphatase (ALP)  $> 1.5 \times ULN$
- AST or ALT  $> 3 \times ULN$  and total bilirubin: (a)  $> 1.5 \times ULN$ , (b)  $> 2 \times ULN$
- AST or ALT  $> 3 \times ULN$  and total bilirubin  $> 2 \times ULN$  and ALP  $< 2 \times ULN$

The summary will include data from all postbaseline visits up to 30 days after the last dose of study drug. For individual laboratory tests, subjects will be counted once based on the most severe postbaseline value. For both the composite endpoint of AST or ALT and total bilirubin, and the composite endpoint of AST or ALT, total bilirubin, and ALP, subjects will be counted once when the criteria are met at the same postbaseline visit date. For randomized phase analysis, the denominator is the number of subjects in the safety analysis set with nonmissing postbaseline value of the tests in evaluation at the same postbaseline visit date. For all B/F/TAF analysis, the denominator is the number of subjects in the ALL B/F/TAF analysis set with nonmissing postbaseline value of the tests in evaluation at the same postbaseline visit date.

Subjects with AST or ALT  $> 3 \times ULN$  will also be listed.

In addition, baseline, postbaseline, and change from baseline in AST, ALT, ALP, and total bilirubin will be summarized by treatment group and visit using descriptive statistics based on the Safety Analysis Set for randomized phase analysis and All B/F/TAF Analysis Set for all B/F/TAF analysis, respectively. Baseline and change from baseline will be compared between the 2 treatment groups using a 2-sided Wilcoxon rank sum test for randomized phase analysis. No formal statistical testing is planned for all B/F/TAF analysis.

In addition, ALT elevation (ie, ALT > 2 x Baseline and ALT > 10 x ULN) and ALT flare, defined as ALT elevations confirmed at two consecutive visits, will be evaluated and listed for subjects with HIV/HBV coinfection at baseline for randomized phase analysis and B/F/TAF phase analysis. The first occurrence of two or more consecutive ALT elevations will be identified as the ALT flare.

## 7.2.5. Renal-Related Laboratory Evaluations

## 7.2.5.1. Serum Creatinine and eGFR $_{CG}$

Baseline, postbaseline, and change from baseline in serum creatinine and eGFRCG will be summarized by treatment group and visit using descriptive statistics based on the Safety Analysis Set for randomized phase analysis and All B/F/TAF Analysis Set for all B/F/TAF analysis, respectively. Baseline and change from baseline will be compared between the 2 treatment groups using a 2-sided Wilcoxon rank sum test for randomized phase analysis. No formal statistical testing is planned for all B/F/TAF analysis.

Median (Q1, Q3) of change from baseline in serum creatinine and eGFRCG over time will be plotted by treatment group based on the Safety Analysis Set for randomized phase analysis and All B/F/TAF Analysis Set for all B/F/TAF analysis, respectively.

Summary of baseline, postbaseline, and change from baseline in serum creatinine and  $eGFR_{CG}$  will be repeated within each subgroup of baseline NRTI backbone based on the Non-Study ARV Medication eCRF (F/TAF vs. F/TDF) based on the Safety Analysis Set for randomized phase analysis. P-values comparing the difference between the 2 treatment groups in baseline values and the change from baseline in metabolic assessment will be generated from a 2-sided Wilcoxon rank sum test for randomized phase analysis.

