Tenofovir (TFV) is a nucleotide analog that inhibits HIV-1 reverse transcription. While tenofovir disoproxil fumarate (TDF), an oral prodrug of TFV, is a preferred NtRTI for initial therapy, nephrotoxicity is an identified risk, and reductions in bone mineral density (BMD) have been shown that are larger than those seen with other nucleoside/nucleotide reverse transcriptase inhibitor (NRTIs). Tenofovir alafenamide (TAF) is also an oral prodrug of TFV. TAF is more stable in plasma than TDF, provides higher intracellular levels of the active phosphorylated metabolite tenofovir diphosphate (TFV-DP), and approximately 90% lower circulating levels of TFV relative to TDF at the clinical doses. The distinct metabolism of TAF offers the potential for an improved clinical profile compared with TDF.

Bictegravir (BIC) (previously referred to as GS-9883) is a potent inhibitor of HIV-1 integrase that is being evaluated for the treatment of HIV-1 infection. Antiviral testing has shown that BIC is active against a broad panel of HIV-1 viral lab strains and clinical isolates. BIC is fully active against a panel of mutant viruses with resistance to NRTIs, non-nucleoside reverse-transcriptase inhibitors (NNRTIs), and protease inhibitors (PIs). Integrase mutant viruses that are resistant to the INSTIs raltegravir (RAL) and elvitegravir (EVG) remain largely sensitive to BIC.

Gilead Sciences (Gilead) has coformulated BIC with the NRTI emtricitabine (FTC; F) and the NtRTI TAF into an FDC tablet that is suitable for once-daily use. This bictegravir/emtricitabine/tenofovir alafenamide (B/F/TAF) FDC may provide a potent, convenient, tolerable, and practical regimen for the long-term treatment of patients with HIV infection.

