#### Randomization

Subjects will be randomized in a 1:1 ratio to 1 of 2 treatment groups (Treatment Group 1: Treatment Group 2). Randomization will be stratified by prior NRTI use (F/TAF vs. F/TDF) and documented or suspected history of NRTI resistance.

NRTI resistance will be stratified by the following categories:

- 1) K65R/E/N, or 3 or more thymidine analogue mutations (TAMs) that include M41L or L210W, or T69 insertions (TAMs are: M41L, D67N, K70R, L210W, T215F/Y, and K219Q/E/R/N)
- 2) Any other pattern of NRTI resistance of M41L, D67N, K70R, L74I/V, Y115F, Q151M, M184I/V, L210W, T215F/Y, K219Q/E/R/N, T69D, K70E/G/M/Q/S/T, V75A/S/M/T
- 3) None of these mutations/no NRTI resistance

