#### 3.3. Strata and Covariates

Randomization was stratified by prior NRTI backbone use (F/TAF vs. F/TDF) and documented or suspected history of NRTI resistance. For analysis, the baseline NRTI resistance stratum was re-classified based on virology data collected at both screening and/or baseline:

Baseline NRTI resistance stratum are as follows:

1) No NRTI mutation:

None of these following mutations/no NRTI resistance

2) K65R/E/N or  $\geq$  3 TAMs:

K65R/E/N or  $\geq$  3 TAMs that include M41L, L210W, or T69 insertions: K65R/E/N, or 3 or more thymidine analogue mutations (TAMs) that include M41L or L210W, or T69 insertions, (TAMs are: M41L, D67N, K70R, L210W, T215F/Y, and K219Q/E/R/N)

3) Any other pattern of NRTI mutation:

Any other pattern of NRTI resistance of M41L, D67N, K70R, L74I/V, Y115F, Q151M, M184I/V, L210W, T215F/Y, K219Q/E/R/N, T69D, K70E/G/M/Q/S/T, V75A/S/M/T

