## 3.4.2. Subject Subgroups for Safety Analyses

- 1) Incidence of all treatment-emergent AEs (TEAEs) will be analyzed for the following subject subgroups (also see Section 7.1.6):
  - Age (years): (a)  $\leq 50$  and (b)  $\geq 50$
  - Sex: (a) male and (b) female
  - Race: (a) black and (b) nonblack
  - Region: (a) US and (b) Ex-US
- 2) Renal-related laboratory tests (ie, serum creatinine and eGFRCG) and fasting metabolic laboratory tests will be analyzed for each subgroup of baseline NRTI backbone: (a) F/TAF (b) F/TDF

- 3) Selected safety endpoints may be analyzed for the following subject subgroups for randomized phase analysis and for all B/F/TAF analyses (see Section 8.1 for details):
  - Subjects with HIV/HBV coinfection at baseline
  - Subjects with incident HIV/HBV coinfection while on study drug (if any)
- 4) Selected safety endpoints will be analyzed for the following subject subgroups for randomized phase analysis and for all B/F/TAF analyses (see Section 8.2 for details):
  - Subjects with HIV/HCV coinfection at baseline
  - Subjects with incident HIV/HCV coinfection while on study drug (if any)

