Baseline height and weight will be used for this calculation.

- 8) SAS codes for the treatment comparison for demographics and baseline characteristics tables.
  - a) CMH test for nominal variable (Y), the p-value from general association test should be used for nominal variable:

```
proc freq order=adsl;
   tables trtgrp * Y /cmh /*general association test*/
run;
```

b) CMH test for ordinal variable (Y), the p-value from row mean score test should be used for ordinal variable:

```
proc freq order=adsl;
   tables trtgrp * Y / cmh2 ; /*row mean score test*/
run;
```

c) Wilcoxon rank sum test for continuous variable (Y), the p-value from the normal approximation two-sided test should be used for continuous variable:

```
proc npar1way wilcoxon data=adsl;
   class trtgrp;
   var Y;
run:
```

9) Please note, "Not Permitted", "Unknown", or missing categories will be excluded percentage calculation and also excluded for p value generation for categorical data analysis (eg, CMH test or Fisher exact test). Except for Mode of infection (HIV Risk Factors), where "Unknown" will be included for percentage calculation, since a subject may fit more than 1 HIV risk factors, therefore percentage may add to more than 100% and no p-value will be generated.

Subjects with Race = "Not Permitted" will also be excluded to define Race subgroup (ie, black vs. nonblack) for efficacy subgroup analysis.

10) SAS code for treatment comparison for duration of exposure. The p-value from log rank test should be used.

```
proc lifetest data=ADSL method=km;
  time TRTDURD*ESDD(0); /*Derive ESDD from COMT01FL, where ESDD = 0
  indicates censored observation (ie, subjects completed study drug)*/
  Strata TRT01AN;
  label TRTDURD = "Duration of Exposure (Days)";
run;
```

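### The pooled renal and fasting metabolic comparisons ignore prior NRTI backbone, a randomisation stratum; if backbone is prognostic, their p-values are somewhat conservative and lose power, by an amount the documents do not fix

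*SAP*

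**What the plan says.** - **Renal (SAP 7.2.5.1):** creatinine and eGFR, at baseline and as change, are compared across the two arms "using a 2-sided Wilcoxon rank sum test for randomized phase analysis".
- **Fasting metabolic (SAP 7.2.3):** the p-values for baseline and change "will be estimated from a 2-sided Wilcoxon rank sum test for randomized phase analysis".
- **Code:** the only Wilcoxon code in the SAP (Appendix 8, item 8, written for the baseline tables) opens "proc npar1way wilcoxon data=adsl" and has treatment as its class variable, with no stratum.
- **Randomisation (SAP 3.3):** "Randomization was stratified by prior NRTI backbone use (F/TAF vs. F/TDF"; NRTI resistance history is the second factor.
- **Subgroups (SAP 3.4.2):** creatinine, eGFR and the fasting metabolic tests "will be analyzed for each subgroup of baseline NRTI backbone". SAP 7.2.3 and 7.2.5.1 carry this out with tables for each backbone. In 7.2.5.1 the subgroup p-value sentence names metabolic assessments instead of renal ones, apparently a phrase carried over from 7.2.3.
- **Status:** SAP 7.2 says formal testing of laboratory data is not foreseen, yet its subsections specify the tests above. The general rule in SAP 3 makes tests two-sided at 5%.

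**The concern.** Under the protocol synopsis, every subject entering on F/TDF moves to a TAF-containing regimen in either arm, while those entering on F/TAF stay on TAF. The protocol background names kidney toxicity as a known TDF risk and says TAF gives "approximately 90% lower circulating levels of TFV relative to TDF at the clinical doses". Creatinine and eGFR may therefore move differently in the two backbone groups whatever the assigned arm.

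Stratified randomisation balances backbone across arms, so backbone adds little to the real variability of the arm difference. An unstratified rank test still counts the spread between backbone groups as noise. The test is then too cautious: its true type I error falls below 5% and it detects real differences less often. Safety and tolerability is the secondary objective, and in a safety comparison this error leans towards finding no difference.

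The separate backbone tables avoid the mixing, but each uses only part of the 565 subjects, and no test combines them.

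**Working it through.** **1. The plan's own figures.** The SAP gives no power, effect size or success criterion for the renal or metabolic comparisons. Its power figures concern the primary endpoint, and they reproduce.
- Normal approximation: n per arm = 2 × 0.02 × 0.98 × (1.960 + 1.282)² / 0.04² = 257.4, so 258 (plan: 260). Power at 260 per arm is 90.3%.
- Exact method: 85.2% with an assumed split of 283/282 (plan: 85% at 565).

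**2. Inputs for this point.**
- From the documents: N = 565 (SAP 1.4 and Appendix 3), 1:1 allocation, two-sided 5%.
- Assumed, because the documents do not give them: prior-F/TDF share f = 10%, 30%, 50%; shift d in the mean change between backbone groups = 0, 0.3, 0.5, 1.0 within-group SD; treatment effect 0.24 SD.
- Scale for eGFR, from the Phase 2 Week 48 quartiles in Protocol 1.2.3.3: SD = IQR/1.349, so (1.6 + 18.7)/1.349 = 15.0 and (24.5 − 0.8)/1.349 = 17.6, root mean square 16.4 mL/min. The median difference there, 11.3 − 7.0 = 4.3 mL/min, is 0.26 SD. Those subjects were treatment-naive, so this only sets a scale: 0.5 SD is about 8 mL/min and 1 SD about 16 mL/min.

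**3. Normal-theory check.** With balanced arms within each backbone group, the unstratified test overstates its standard error by √r, where r = 1 + f(1 − f)d². True size = 2[1 − Φ(1.96√r)]. If the stratified test has 80% power, unstratified power = Φ(1.96 + 0.842 − 1.96√r).
- f = 0.3, d = 0.5: r = 1 + 0.21 × 0.25 = 1.0525, √r = 1.026, size 0.044, power 78.5%.
- f = 0.5, d = 1.0: r = 1.25, √r = 1.118, size 0.028, power 72.9%.

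**4. Simulation** (20,000 trials per cell, normal outcomes, balanced arms within backbone). Entries are for f = 10% / 30% / 50%. Losses come from unrounded values.

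| Shift d | Unstratified type I error | Unstratified power, % | van Elteren power, % | Loss, points |
|---|---|---|---|---|
| 0 | 0.0476 / 0.0488 / 0.0496 | 79.3 / 79.7 / 79.4 | 79.2 / 79.5 / 79.3 | none |
| 0.3 | 0.0504 / 0.0484 / 0.0483 | 78.9 / 79.2 / 79.2 | 78.9 / 79.7 / 79.5 | 0.1 / 0.5 / 0.3 |
| 0.5 | 0.0485 / 0.0460 / 0.0470 | 79.0 / 78.4 / 78.0 | 79.3 / 79.5 / 79.3 | 0.3 / 1.2 / 1.3 |
| 1.0 | 0.0395 / 0.0312 / 0.0268 | 77.0 / 74.0 / 72.7 | 79.2 / 79.8 / 79.6 | 2.2 / 5.9 / 6.8 |

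The van Elteren type I error stays between 0.047 and 0.054. Simulation error is about 0.0015 for type I error and 0.3 points for power. At d = 0.5 the formula gives slightly more conservatism than the simulation (size 0.043-0.048, loss 0.6-1.7 points); the conclusion is the same.

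**The case against.** The strongest reply is that nothing depends on these p-values. Protocol 8.6.3 plans descriptive laboratory summaries, multiplicity control in SAP 3.5 covers only the two Week 48 HIV-1 RNA endpoints, and no decision rule uses the renal or metabolic tests. The within-backbone tables already show a reader the effect free of mixing. This limits the importance of the point. It does not remove it: the two subsections still specify between-arm tests, and separate subgroup p-values do not replace a combined one.

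A second reply is that the loss is conjectural. This stands in part. Without the F/TDF share and the shift, no figure can be fixed, and nothing in the documents supports a shift as large as 1 SD. The simulation also assumes exact balance within backbone; any imbalance would weaken the conservatism.

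A third concerns timing. SAP 2.2.1 records the Week 48 analysis as done, and this SAP governs the final analysis. Replacing a test now would be a change after unblinded results, and could leave final p-values that do not match earlier ones if the same test was used at Week 48. This stands, and it rules out substitution.

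**Conclusion.** The pooled tests leave out a factor on which randomisation was stratified. If that factor is prognostic, they are conservative and less powerful than a stratified test. Under the assumed shares and treatment effect, the loss is about 1 point or less up to a shift of 0.5 SD, and reaches 2-7 points only near 1 SD. This is a minor improvement, not an error in a stated figure.

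A reader might infer more, without support from the documents:
- **That the p-values are conservative as a matter of fact.** This needs a backbone effect whose existence and size are not given; with no shift there is no loss.
- **That backbone is known to drive lipid changes.** The background passage speaks of kidney, bone and circulating tenofovir, not lipids. Planning a subgroup table shows that the question is examined, not that a difference is expected.
- **That false positives are inflated.** The direction is the opposite.

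**What to change.** In SAP 7.2.3 and 7.2.5.1, add a van Elteren (stratified Wilcoxon) test of change from baseline in fasting metabolic tests, serum creatinine and eGFR, with baseline backbone derived from the Non-Study ARV Medication eCRF as the stratum. In SAS this is PROC FREQ on backbone*treatment*change with CMH2 and SCORES=MODRIDIT. Report it beside the planned Wilcoxon test and label it as added after the Week 48 analysis. Keep the by-backbone tables. In the same edit, make the subgroup p-value sentence in 7.2.5.1 refer to the renal measures.

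The cost is a few lines of code, since the stratum is already derived for the baseline tables, and a second nominal p-value per comparison that readers must not choose between. If backbone proves not to be prognostic, the simulation shows essentially no power lost by stratifying.

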#### 7.3. Body Weight, Height, and Vital Signs

Descriptive statistics will be provided by treatment group for vital signs and body weight as follows based on the Safety Analysis Set for randomized phase analysis and All B/F/TAF Analysis Set for all B/F/TAF analysis, respectively:

- Baseline values
- Values at each postbaseline analysis window
- Change from baseline to each postbaseline analysis window

A baseline value will be defined as the last nonmissing value obtained on or prior to the date of first dose of study drug. Change from baseline to a postbaseline visit will be defined as the postbaseline value minus the baseline value.

In the case of multiple values in an analysis window, data will be selected for analysis as described in Section 3.8.3. No formal statistical testing is planned.

A by-subject listing of vital signs will be provided by subject ID number and visit in chronological order. In the same listing, a by-subject listing of body weight, height, and BMI will be provided.

#### 7.4. Prior and Concomitant Medications

## 7.4.1. Nonstudy Drug Antiretroviral Medications

Any nonstudy drug ARV medications used prior to, during, or after the study (if collected) will be coded using the Gilead-modified WHO Drug Dictionary for ARV medications. The WHO preferred drug name and drug code will be attached to the clinical database. All nonstudy drug ARV medications will be listed. No inferential statistics will be provided.

